### **Ethical and Regulatory Requirements**

The principles for ethical and regulatory requirements for the study, including this genetics research component, are outlined in Section 7 of the protocol.

### **Informed consent**

The genetic component of this study is optional and the subject may participate in other components of the main study without participating in the genetic component. To participate in the genetic component of the study the subject must sign and date both the consent form for the main study and the genetic component of the study. Copies of both signed and dated consent forms must be given to the subject and the original filed at the study site. The Principal Investigator(s) is responsible for ensuring that consent is given freely and that the

subject understands that they may freely discontinue from the genetic aspect of the study at any time.

### **Subject data protection**

AstraZeneca will not provide individual genotype results to subjects, any insurance company, any employer, their family members, general physician unless required to do so by law.

Extra precautions are taken to preserve confidentiality and prevent genetic data being linked to the identity of the subject. In exceptional circumstances, however, certain individuals might see both the genetic data and the personal identifiers of a subject. For example, in the case of a medical emergency, an AstraZeneca Physician or an investigator might know a subject's identity and also have access to his or her genetic data. Also, Regulatory authorities may require access to the relevant files, though the subject's medical information and the genetic files would remain physically separate.

### **Data management**

Any genotype data generated in this study will be stored at a secure system at AstraZeneca and/or designated organizations to analyze the samples.

The results from this genetic research may be reported in a separate report from the CSR or published in scientific journals.

AstraZeneca and its designated organizations may share summary results (such as genetic differences from groups of individuals with a disease) from this genetic research with other researchers, such as Hospitals, Academic Organization or Health Insurance Companies. This can be done by placing the results in scientific databases, where they can be combined with the results of similar studies to learn even more about health and disease. The researchers can only use this information for health related research purposes. Researchers may see summary results but they will not be able to see individual subject data or any personal identifiers.

Some or all of the clinical datasets from the main study may be merged with the genetic data in a suitable secure environment separate from the clinical database.

### **Statistical Methods and Determination of Sample Size**

The number of subjects that will agree to participate in the genetic research is unknown. It is therefore not possible to establish whether sufficient data will be collected to allow a formal statistical evaluation or whether only descriptive statistics will be generated. A Statistical Analysis Plan will be prepared where appropriate.

## **Appendix E Patient Treatment Guidelines**

### **Hyperkalemia**

Subjects will have their serum potassium measured by a Central Laboratory. If the serum potassium is between 5.6 and 5.9 mEq/L, inclusive (5.6 to 5.9 mmol/L), application of standard clinical assessment and care for the medical circumstance at hand should be implemented. Assuming that the result represents a true case of hyperkalemia, corrective measures should be initiated to prevent further increases in serum potassium, including review of the patient's dietary intake, any use of nonsteroidal anti-inflammatory drugs (NSAIDs), use of potassium-sparing medications, and use of potassium supplements. The need for diuretics, sodium polystyrene sulphonate and/or acute therapies may need to be considered. The ACEi or ARB dose may also need to be reduced, but this should be done only after review with the medical monitor.

If the serum potassium measured by the Central Laboratory is  $\geq 6.0$  mEq/L (6.0 mmol/L), immediate measures must be carried out to determine the cause and corrective actions instituted. Decisions to adjust or discontinue the ACEi and ARB will be at the discretion of the Principal Investigator and the medical monitor.

If after corrective measures are taken, including temporary discontinuation of ACEi or ARB, in a patient who has a serum potassium of  $\geq 6.0$  mEq/L (6.0 mmol/L), and the potassium fails to decrease to  $\leq 5.5$  mEq/L (5.5 mmol/L), the ACEi or ARB must be discontinued permanently and the medical monitor should be notified.

Subjects who discontinue ACEi or ARB may remain on investigational drug following consultation with the medical monitor and should be followed for the full duration of the study.

## **Appendix F COVID-19 Specifics**

### **F 1 Background to COVID-19**

There is currently an outbreak of respiratory disease (COVID-19) caused by a novel SARS-CoV-2 that was first detected in Wuhan City, Hubei Province, China in 2019. This new virus has rapidly spread across the globe causing the World Health Organisation to declare a pandemic situation on 12 March 2020. The countermeasures initiated by national and local governments worldwide and the recommendations issued by the health authorities have impacted current and new clinical studies. As the threat of pandemic burden including new outbreaks, locally or globally, will impact the further conduct of clinical studies, appropriate risk assessments and mitigation measures will need to be taken into consideration in all clinical studies to protect subjects, site staff, and society as a whole.

Both European Medicines Agency (EMA) and Food and Drug Administration (FDA) as well as national health authorities in Europe have issued new guidelines that aim to provide recommendations for actions for conduct of clinical studies of medical products during COVID-19 pandemic. Since the pandemic situation is evolving, guidelines, recommendations, national laws, and local restrictions may change at high pace. Given the circumstances of potentially relapsing pandemic or epidemic situation with regard to the spread of COVID-19 in future, special attention will be paid to protect subjects participating in the study and site staff involved in the investigations against infection with SARS-CoV-2 as requested by the newly issued EMA guideline.

### **F 2 Risk Assessment for COVID-19 Pandemic**

There are 2 investigational products with different mechanisms of action that are unlikely to impact on the course of infection with SARS-CoV-2. MEDI3506 does have an anti-inflammatory mode of action with inhibition of IL-33 and prevention of binding to its receptor ST2. While this poses a theoretical risk of adversely influencing the antiviral response, this is judged to be unlikely. Dapagliflozin is an anti-glycemic agent and is believed not to cause immune suppression. Therefore, risk of the subjects exposed to SARS-CoV-2 or to suffer from COVID-19 is expected to be similar to the background population with the same co-morbidities as those in the study, in particular CKD and T2DM. The risk of exposure to infected people cannot be completely excluded as the subjects may need to expose themselves to public areas (eg, commute to the site) and have additional human contact (eg, with site staff and other subjects of the clinical study).

Measures to mitigate the additional risks caused by COVID-19 are:

- This study will resume enrolling only when the sponsor and contract research organization in collaboration deem it is safe to start the study. In addition, the study will not resume until the local confinement measures or other safety restrictions linked to the

COVID-19 pandemic imposed by the local authorities are compatible with safe conduct of the study.

- Current national laws and local recommendations for prevention of pandemic will be strictly adhered to.
- Subjects will be closely monitored for any signs and symptoms of COVID-19, including fever, dry cough, dyspnea, sore throat and fatigue throughout the study during the pandemic. Once clinical signs of infection are reported by subjects, the investigator needs to determine whether samples can be collected, and safety data can be recorded on site. If not, AEs and concomitant medications will be obtained via phone calls. The decision to continue with dosing the subject with the study drugs in the event of him/her showing symptoms of COVID-19 infection will be per investigator's discretion.
- If, for reasons related to the COVID-19 pandemic, a subject is not able to attend their scheduled visit within the visit window, they can have their visit rescheduled within 14 days of the original scheduled visit; however, visits that cannot be rescheduled within a 14-day window must be skipped and subjects should continue at the next scheduled visit.
- During the COVID-19 pandemic, on-site visits may be replaced by a telemedicine visit if allowed by local/regional guidelines. Having a telemedicine contact with the subjects will allow collection of data for AEs, concomitant medications, adherence to the eDiary and patient-reported outcome measures to be reported and documented. The term telemedicine visit refers to remote contact with the subjects using telecommunications technology including phone calls, virtual or video visits, and mobile health devices.
- The probability of virus transmission will be controlled as much as possible by:
  - Advising subjects to adhere to local requirements for reduction of the public exposure while ambulatory.
  - Assessment of potential COVID-19 infection by optional laboratory assessment based on availability (test capacity and turnaround time) of approved tests and on investigator's discretion.
  - Requesting all subjects to be contacted by phone 1 day prior to every visit for assessing COVID-19 symptoms and signs and asking subjects to not attend the site in case of suspected reports. In addition, sites will ask subjects regarding any contact with a person who has tested positive for SARS-CoV-2. If applicable, subjects will be referred to the local healthcare system for further follow-up and treatment.
  - Applying physical distancing and person-to-person contact restrictions during site visits and in-house confinement.
  - Use of personal protective equipment by study subjects (surgical face mask, gloves) and staff (for example but not limited to masks, gloves, protectors, medical suits)

where physical distancing is not possible if deemed appropriate by the investigators and site staff and guided by local requirements.

- Implementation of logistical improvements of the site and structural measures of the study site building to further improve physical distancing.

### **F 3 Restrictions Related to COVID-19**

During the COVID-19 pandemic, subjects are advised to adhere to local requirements for reduction of the public SARS-CoV-2 exposure while ambulatory. If applicable, prior to Screening Visit 1, potential subjects should be called to confirm they are not experiencing any COVID-19 symptoms and signs and are asked not to attend the site in case of suspected infection. If appropriate, subjects will be referred to the local healthcare system. Physical distancing and person-to-person contact restrictions will be applied and explained to subjects while staying at the study site. Where physical distancing is not possible, study subjects will be asked to use surgical face masks and/or gloves if deemed appropriate by the investigator and site staff and guided by local requirements.

### **F 4 Data Quality Assurance Related to COVID-19**

Monitoring visits at site will be limited to a minimum required as deemed appropriate during COVID-19 pandemic, per local regulations.

In addition, where possible, other measures for carrying out protocol-related activities, such as but not limited to home nursing and safety clinical laboratory tests performed in a local licensed laboratory, may be employed as required.

## **Appendix G Changes Related to Mitigation of Study Disruptions Due to Cases of Civil Crisis, Natural Disaster, or Public Health Crisis**

**Note:** Changes below should be implemented only during study disruptions due to any of or a combination of civil crisis, natural disaster, or public health crisis (eg, during quarantines and resulting site closures, regional travel restrictions and considerations if site personnel or study patients become infected with SARS-CoV-2 or similar pandemic infection) during which patients may not wish to or may be unable to visit the study site for study visits. These changes should only be implemented if allowable by local/regional guidelines and following notification from the sponsor and instructions on how to perform these procedures will be provided at the time of implementation.

### **G 1 Reconsent of Study Patients During Study Interruptions**

During study interruptions, it may not be possible for the patients to complete study visits and assessments on site and alternative means for carrying out the visits and assessments may be necessary, eg, remote visits. Reconsent should be obtained for the alternative means of carrying out visits and assessments and should be obtained prior to performing the procedures described in Sections G 2 to G 6. Local and regional regulations and/or guidelines regarding reconsent of study patients should be checked and followed. Reconsent may be verbal if allowed by local and regional guidelines (note, in the case of verbal reconsent the ICF should be signed at the patient's next contact with the study site). Visiting the study sites for the sole purpose of obtaining reconsent should be avoided.

### **G 2 Rescreening of Patients To Reconfirm Study Eligibility**

Additional rescreening for screen failure due to study disruption can be performed in previously screened subjects. The investigator should confirm this with the designated Study Physician.

In addition, during study disruption there may be a delay between confirming eligibility of a patient and either enrollment into the study or commencing of dosing with IP. If this delay is outside the screening window specified in Section 4.2.1, the patient will need to be rescreened to reconfirm eligibility before commencing study procedures. This will provide another opportunity to re-screen a patient in addition to that detailed in Section 4.2.1. The procedures detailed in Section 4.2.1 must be undertaken to confirm eligibility using the same randomization number as for the patient.

### **G 3 Home or Remote Visit to Replace On-site Visit (where applicable)**

A qualified HCP from the study site or TPV service will visit the patient's home / or other remote location as per local SOPs, as applicable. Supplies will be provided for a safe and efficient visit. The qualified HCP will be expected to collect information per the CSP.

### **G 4 Telemedicine Visit to Replace On-site Visit (where applicable)**

In this appendix, the term telemedicine visit refers to remote contact with the patients using telecommunications technology including phone calls, virtual or video visits, and mobile health devices.

During a civil crisis, natural disaster, or public health crisis, on-site visits may be replaced by a telemedicine visit if allowed by local/regional guidelines. Having a telemedicine contact with the patients will allow adverse events and concomitant medication to be reported and documented. If applicable, safety procedures and blood sample collection will be performed according to the revised SoA in the Study Instructions for Mitigation Due to Civil Crisis, Natural Disaster, or Public Health Crisis.

### **G 5 At-home or Remote Location Investigational Product Administration Instructions**

If a site visit is not possible, at-home or remote location administration of investigational product may be performed by a qualified HCP, provided this is acceptable within local regulation/guidance, or by the patient or his/her caregiver. The option of at-home or remote location investigational product administration ensures patients safety in cases of a pandemic where patients may be at increased risk by traveling to the site/clinic. This will also minimize interruption of investigational product administration during other study disruptions, eg, site closures due to natural disaster.

#### **G 5.1 At-home or Remote Location Investigational Product Administration by a Qualified HCP or TPV Service**

A qualified HCP from the study site or TPV service should administer the investigational product at the patient's home or other remote location according to the CSP. All necessary supplies and instructions for administration and documentation of investigational product administration will be provided. Additional information related to the visit can be obtained via a telemedicine or home visit.

#### **G 5.2 At-home or Remote Location Investigational Product Administration by the Patient or His/Her Caregiver**

Prior to at-home or remote location investigational product administration the investigator must assess the patient or his/her caregiver to determine whether they are appropriate for at-

home or remote location administration of investigational product. Once the patient or his/her caregiver is deemed appropriate for at-home or remote location administration, he/she must receive appropriate training. All necessary supplies and instructions for administration and documentation of investigational product administration will be provided. More information related to the visit can be obtained via a telemedicine or home / remote visit.

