### 3.1.3 Study Conduct Mitigation During Study Disruptions Due to Cases of Civil Crisis, Natural Disaster, or Public Health Crisis

The guidance given below supersedes instructions provided elsewhere in this protocol and should be implemented only during cases of civil crisis, natural disaster, or public health crisis (eg, during quarantines and resulting site closures, regional travel restrictions, and considerations if site personnel or study subjects become infected with SARS-CoV-2 or similar pandemic infection) which would prevent the conduct of study-related activities at study sites, thereby compromising the study site staff or the subject's ability to conduct the study. The investigator or designee should contact the study sponsor to discuss whether the mitigation plans below should be implemented.

To ensure continuity of the clinical study during a civil crisis, natural disaster, or public health crisis, changes may be implemented to ensure the safety of study subjects, maintain compliance with Good Clinical Practice, and minimize risks to study integrity.

Where allowable by local health authorities, ethics committees, healthcare provider guidelines (eg, hospital policies) or local government, these changes may include the following options:

- Obtaining consent for the mitigation procedures (note, in the case of verbal consent, informed consent form (ICF) should be signed at the subject's next contact with the study site).

- Rescreening: Additional rescreening for screen failure and to confirm eligibility to participate in the clinical study can be performed in previously screened subjects. The investigator should confirm this with the designated Study Physician.
- Home or Remote visit (when applicable): Performed by a site qualified Healthcare Professional (HCP) or HCP provided by a third-party vendor (TPV).
- Telemedicine visit: Remote contact with the subjects using telecommunications technology including phone calls, virtual or video visits, and mobile health devices.

For further details on study conduct during civil crisis, natural disaster, or public health crisis, refer to Appendix G.

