**Table 6 Schedule of Treatment Period Study Procedures**

Study Period	Treatment Period							Early D/c Visit
Visit Number	V3	V4	V5	V6	V7	V8	V9	
Procedure / Study Day	Day 1	Day 29 (± 5 days)	Day 57 (± 5 days)	Day 85 (± 5 days)	Day 113 (± 5 days)	Day 141 (± 5 days)	Day 169 (± 5 days)	

- a Including focused cardiac exam (Section 4.3.2.2).
- b For the first 2 doses of MEDI3506 or placebo, patients are to remain at the site for  $\geq 2$  hours or until stable, whichever is later. In addition, vital signs will be taken before and immediately after administration of MEDI3506 or placebo, and at 30 minutes ( $\pm 5$  minutes) as well as 120 minutes ( $\pm 10$  minutes) thereafter or until stable, whichever is later. Following the observation period, subject discharge will be at the discretion of the investigator. For all other dosing visits, vital signs will be collected 30 minutes ( $\pm 5$  minutes) after administration of MEDI3506 or placebo or when stable.
- c May be performed independently of other Visit 9 procedures within the visit window.
- d PK samples on MEDI3506/placebo dosing days will be collected pre-dose of MEDI3506/placebo administration.
- e Dapagliflozin PK samples will be collected at the following time points relative to dapagliflozin administration: Day 141 (predose and 2 h postdose) and Day 169 on study visit. Patients will be reminded to take dapagliflozin on site visits during dapagliflozin administration time (Day 85 to Day 168/Visit 6 to Visit 8).

- g If consent obtained.
- h After randomization. If, for any reason, the sample is not drawn pre-dose on Visit 3 (Day 1), it may be taken at any visit until the final follow-up visit/Early Discontinuation Visit.
- i Subjects collect 3 consecutive first morning void midstream urine samples (ideally day of visit and preceding 2 days [refrigerated overnight]) which are returned on the day of visit.
- j In the event that a dose cannot be administered within the window of the scheduled dosing date, the dose may be administered outside of the dosing window as long as it is at least 14 days prior to the next dose and recorded as a protocol deviation.
- k Subjects enrolled that have reached the Day 85 visit prior to Amendment 2 approval should continue in the study without the addition of dapagliflozin to their dosing regimen.

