#### **4.3.2.3 Vital Signs**

BP will be measured at each study visit along with other vital signs of temperature, pulse, and respirations. The nominal timing of vital signs, ECGs, and blood draws is described (Section 4.2). Whenever vital signs, 12-lead ECGs, and blood draws are scheduled for the same nominal time, the blood draws should occur last.

For the first 2 doses of MEDI3506 or placebo, vital signs will be taken before and immediately after administration of investigational product, and at 30 minutes ( $\pm 5$  minutes) as well as 120 minutes ( $\pm 10$  minutes) thereafter or until stable, whichever is later. Following the observation period, subject discharge will be at the discretion of the investigator. For all other dosing visits, vital signs will be collected 30 minutes ( $\pm 5$  minutes) after administration of MEDI3506 or placebo or when stable.

The subject should be in a seated or supine position for at least 10 minutes prior to the collection of vital signs, as follows:

- Oral, axillary, or tympanic temperature
- Diastolic BP
- Systolic BP
- Heart (pulse) rate
- Respiratory rate

For each BP measurement, the same arm and the same appropriately sized BP cuff should be used.

Vital signs are to be recorded in the EDC system. Vital signs may be repeated once after an additional 5 minutes of rest. Clinically significant abnormalities in vital signs will be recorded as AEs.

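### Appendix G 5.2 lets a patient or caregiver give investigational product at home without excluding the first 2 MEDI3506/placebo doses, so dose 2 (Day 29) could be given without the 2-hour stay and vital signs

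*Protocol*

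**What the plan says.** Appendix G 5 provides that, when a site visit is not possible, investigational product may be given at home or another remote location by a qualified healthcare professional (HCP), "or by the patient or his/her caregiver".

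G 5.2 sets the conditions for the patient or caregiver. The investigator first judges suitability, and then: "Once the patient or his/her caregiver is deemed appropriate for at-home or remote location administration, he/she must receive appropriate training". Supplies and instructions are to be provided. On contact around the dose it says only: "More information related to the visit can be obtained via a telemedicine or home / remote visit". It names no dose number, observation time or vital signs.

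G 5.1, on dosing by an HCP, says that the product is given at the patient's "home or other remote location according to the CSP". G 5.2 has no matching phrase.

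On precedence, Section 3.1.3 states: "The guidance given below supersedes instructions provided elsewhere in this protocol". It refers to Appendix G for details.

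The normal rule is in two places. Table 6 footnote b: "For the first 2 doses of MEDI3506 or placebo, patients are to remain at the site for" at least 2 hours, or until stable if that is later. Section 4.3.2.3: "For the first 2 doses of MEDI3506 or placebo, vital signs will be taken before and immediately after administration of investigational product", then again at 30 and 120 minutes. Section 4.5.1.5 requires treatment for anaphylaxis to be at hand and study personnel to be trained to recognize and treat it.

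**The concern.** The protocol places the first 2 injections under closer watch than the rest. Dose 2 is the subject's first re-exposure to the antibody. Serious hypersensitivity is a named potential risk in Section 1.7.1 and an adverse event of special interest in Section 5.3. The benefit-risk argument in Section 1.7.1 relies partly on clinical monitoring and on sites equipped to manage anaphylaxis.

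A subject dosed at home by a caregiver cannot also remain at the site, so the two rules cannot both be followed. If the disruption guidance prevails, the closer watch over dose 2 is lost and G 5.2 puts nothing in its place. The route has several gates: a disruption, sponsor notification, local permission, reconsent, suitability assessment and training. None of them supplies observation after the injection.

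**Working it through.** No figure in the protocol needs reproducing. The check compares the rules, then confirms that the alternatives for dose 2 fit the visit schedule.

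**1. Which doses are affected.** Table 6 schedules MEDI3506/placebo at Visits 3 to 8: Days 1, 29, 57, 85, 113 and 141, that is 6 doses 28 days apart. The closer watch applies to Days 1 and 29. Day 1 is also the randomization visit, so in practice it is done on site. The exposed dose is Day 29.

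**2. The rules for dose 2.**

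| Item | Normal conduct (Table 6 footnote b, 4.3.2.3) | Patient or caregiver at home (G 5.2) |
|---|---|---|
| Place | Site | Home or remote location |
| Stay after the dose | At least 2 hours, or until stable if later | None stated |
| Vital signs | 1 before + 3 after (immediately, 30 min, 120 min) = 4 time points | None stated |
| Contact | Site staff present | Optional and untimed |
| Dose excluded | Not applicable | None |

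**3. Which rule prevails.** Section 3.1.3 puts the disruption guidance above the rest of the protocol and lists nothing that survives. G 5.2 does not refer back to the protocol, whereas G 5.1 does. The visible text therefore allows dose 2 at home without the footnote b observation.

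**4. Whether MEDI3506/placebo is covered.** G 5 uses the general term for investigational product and does not confine it to dapagliflozin. Section 4.5.4 already treats home self-administration of dapagliflozin as normal conduct, so a suitability assessment and training would add little if only the tablets were meant.

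**5. Whether rescheduling dose 2 is feasible.** Section 4.1.6.1 allows dosing within 14 days of a missed visit. Table 6 footnote j requires at least 14 days before the next dose. Counting from nominal Day 29:

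- Latest dose 2: 29 + 14 = Day 43.
- Gap to nominal dose 3: 57 − 43 = 14 days, which just meets the minimum.
- Gap at the early edge of the Visit 5 window (57 − 5 = Day 52): 52 − 43 = 9 days, too short.
- Gap at the late edge (57 + 5 = Day 62): 62 − 43 = 19 days, acceptable.

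Rescheduling works, but after a Day 43 dose the next one must fall on Day 57 or later.

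**The case against.** The strongest reply is that silence in a contingency appendix is not permission. The options listed in Section 3.1.3 name an HCP for home visits and do not mention self-administration, which enters only through the reference to Appendix G. G 5.2 waives nothing expressly. Read together, footnote b could still hold dose 2 at the site. That reading is possible, but no visible sentence keeps footnote b in force, and Section 3.1.3 points the other way.

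Second, it is doubtful that patient or caregiver injection of MEDI3506/placebo was thought through. Section 4.5.4 has site personnel administer it. Section 4.6.1 has an unblinded product manager prepare it. Section 4.6.2 says that active and placebo differ in appearance or viscosity, and that someone outside the subject's management gives it. This conflict is real, but it does not confine G 5.2 to dapagliflozin.

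Third, the details may lie elsewhere. The note to Appendix G says that "instructions on how to perform these procedures will be provided at the time of implementation". G 4 refers to a revised schedule in separate instructions, and parts of Section 4.5.1 are redacted. Any of these could restore the safeguards. This limits confidence in the point, but the visible protocol does not require them to do so.

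Fourth, the exposure is narrow. A disruption would have to cover Day 29 and make HCP dosing at home and rescheduling impracticable or unused. A caregiver, or a home visit, may also be present. This stands, and it bears on severity.

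**Conclusion.** The point holds as a gap in the protocol text: G 5 and G 5.2, with the precedence given by Section 3.1.3, allow dose 2 of MEDI3506/placebo at home without the 2-hour stay and the 4 vital-sign time points. It is a minor to moderate safety point and does not affect the endpoint, power or analysis. It assumes that investigational product in G 5 includes MEDI3506/placebo and that no unseen instruction already bars the first 2 doses.

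A reader might infer three stronger things, none of which the documents support:

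- That the anaphylaxis requirement of Section 4.5.1.5 lapses at home. G 5.2 is silent on it and Section 4.5.1.5 is not tied to a place, so its status is unclear rather than revoked.
- That dose 2 would be given with nobody watching. A caregiver may give the dose and a home visit is available. What is missing is any requirement to observe.
- That a rate of harm can be attached. The protocol gives neither the number of doses likely to be given this way nor any reaction data for a home-administered second dose.

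**What to change.** Amend G 5.2 to state that the first 2 MEDI3506/placebo doses may not be given by the patient or caregiver. They are to be:

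- given on site; or
- given by an HCP under G 5.1, who stays at least 2 hours and takes the footnote b vital signs; or
- rescheduled within 14 days under Section 4.1.6.1, with at least 14 days to the next dose.

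Add one sentence stating that Section 4.5.1.5 is not superseded by the disruption guidance.

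This wording should not be taken to endorse patient or caregiver injection of the later MEDI3506/placebo doses. The conflict with Sections 4.5.4, 4.6.1 and 4.6.2 is a separate matter for the sponsor to settle.

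The cost is a few sentences in an amendment and an occasional delayed or missed dose 2 during a disruption. Section 4.1.6.1 tolerates one missed dose. A second one means discontinuation, so a subject who misses dose 2 has no further allowance.
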